## 4.2 Study Endpoints

### 4.2.1 Primary Study Endpoints

Clinical effectiveness endpoint

- Result Accuracy: Clinical relation between HemoPill acute measurement (trial procedure) and endoscopic findings (control procedure) according to the defined scenarios for “true positive”, “false positive”, “true negative”, “false negative” (see above, chapter 4.1).

### 4.2.2 Secondary Study Endpoints

Technical effectiveness endpoint

Technical success, defined as:

- Successful data transmission of the HemoPill acute to the HemoPill Receiver.

Safety endpoints:

Adverse events / complications associated with trial or control procedure, such as:

Trial procedure:

- Aspiration of the capsule on ingestion
- Delayed excretion, or failure to excrete the capsule (capsule retention)
- Obstruction of the digestive tract
- Injury to tissue structures during the passage of the HemoPill acute through the digestive tract.

Control procedure:

- Cardiopulmonary adverse events
- Infection
- Perforation
- Bleeding (iatrogenic)

These secondary endpoints were chosen as they potentially provide meaningful information on the safety (number and type of adverse events / complications) and performance (successful data transmission) of the subject device.

### 4.2.3 Exploratory Endpoints

Not applicable.

## 5 Study Enrollment and Withdrawal

### 5.1 Inclusion Criteria

In order to be eligible to participate in this study, an individual must meet all of the following criteria:

1. Patient is scheduled for endoscopy due to suspicion of UGIB based on clinical and / or laboratory findings
2. Signed informed consent
3. Age  $\geq$  18 years
4. Willingness and ability to participate in the study procedure

### 5.2 Exclusion Criteria

An individual who meets any of the following criteria will be excluded from participation in this study:

1. The inclusion criteria cannot be met

2. Contraindications to the use of the HemoPill acute, such as:
  - a. Known gastrointestinal obstruction, stricture, fistula, or diverticula
  - b. Dysphagia or other swallowing disorders
  - c. Pregnancy
  - d. Incapacity to provide informed consent
  - e. In patients with cardiac pacemakers and other implanted medical devices

### ***5.3 Vulnerable Subjects***

No vulnerable subjects are to be included in the clinical trial.

### ***5.4 Strategies for Recruitment and Retention***

The patient may be recruited from both inpatient and outpatient setting. Patient will be identified by our gastroenterology inpatient consult team when a consult for upper gastrointestinal bleeding has been suspected on admission or by an outpatient provider that is part of the study when they see the patient in their perspective clinics. Patients for suspected upper GI bleed will be asked by a study member of his/her willingness to participate in the study. The target number for subject recruitment is 50. The study team will not be using Epic as part of the recruitment process.

All subjects will be recruited from the PI and sub-investigators' practices or under their care in the inpatient setting. Potential subjects will be approached at one of their clinic visits by the PI, sub-investigator or research coordinator. Potential subjects will be approached after suspicion of a GI bleed led to the scheduling of endoscopy. Patient will be consented prior to scheduled endoscopy and sedation. Time between approaching potential subjects and onset of study procedures may vary as this depends on the scheduling of endoscopy. Scheduling for endoscopy is influenced by, e.g., urgency of the patient's situation and availability. It is not influenced by willingness or unwillingness to participate in the study. No recruitment materials are needed for this process.

### ***5.5 Duration of Study Participation***

From screening a likely trial participant to enrollment and to conclusion of the endoscopic procedure, usually 1 hours to 3 days elapse. Screening of a potential trial participant occurs after a NYU patient is scheduled for endoscopy for a suspected UGIB. Scheduling of endoscopy is at the attending physician's discretion and not within the scope of the trial. If patient screening is successful and informed consent is obtained, the study intervention phase starts approximately 20 minutes to 1 hour prior to endoscopy. The study intervention phase finishes with conclusion of endoscopy. No trial related follow-up is required. Scheduling further appointments to follow-up on endoscopic findings are not within the scope of the clinical trial.

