Endpoint	
Effectiveness Endpoints:
 
 
- Technical effectiveness endpoint
 
 
Technical success, defined as:
 
Successful data transmission of the HemoPill acute to the HemoPill Receiver
 
 
- Clinical effectiveness endpoint
 
 
Result accuracy: Clinical relation between HemoPill acute measurement (trial procedure) and endoscopic findings (control procedure) according to defined events for true positive, true negative, false positive, false negative.
 
Safety Endpoints:
 
 
- Adverse events / complications associated with trial or control procedure, such as:
 
 
Trial procedure:
 
 
○ Aspiration of the capsule on ingestion
 
○ Delayed excretion, or failure to excrete the capsule (capsule retention)
 
○ Obstruction of the digestive tract
 
○ Injury to tissue structures during the passage of the HemoPill acute through the digestive tract. In particular, this may involve: 
 
■ Injury to the mucosa
 
■ Bleeding, e.g., variceal bleeding
 
■ Perforations
 
 
 
 
Control procedure:
 
 
○ Cardiopulmonary adverse events
 
○ Infection
 
○ Perforation
 
○ Bleeding (iatrogenic)
 

Study Duration	March 18, 2022 to July 31 st , 2022
Participant Duration	Single visit, patient participation ends with conclusion of endoscopy
Population	Adult subjects (meeting inclusion criteria) with suspected UGIB due to clinical and / or laboratory findings and therefore scheduled for endoscopy
Study Sites	NYU Langone Health [name]
Number of participants	Recruitment goal: 50 Patients; Statistical validity reached at 43 Patients w/o dropouts.

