### **Risks to participants by virtue or trial participation**

- Immediate risks
  - o Aspiration of the capsule on ingestion
  - o Obstruction of the digestive tract
  - o Injury to tissue structures during the passage of the HemoPill acute through the digestive tract. In particular:
    - Injury to the mucosa
    - Bleeding, e.g., variceal bleeding
    - Perforations
- Long-range risks
  - o Obstruction of the digestive tract
  - o Delayed excretion, or failure to excrete the capsule (capsule retention)

- Necessity of exposing human participants to above-mentioned risks

The above-mentioned risks are generally associated with capsule endoscopy, e.g., video capsule endoscopy. As of today, no incidence of patient harm from use of HemoPill has been reported. Within the trial context, HemoPill is ingested in a closely supervised setting. Within the trial context, a HemoPill measurement does not influence the clinical course of a given trial participant. Thus, any hypothetical risks from false negative or false positive measurements are avoided.

On the other hand, investigating HemoPill's capacity for reliably providing information on the presence or absence of blood in the GI lumen has the potential to better understand the clinical applicability of the device and provide information on the proposed clinical benefit. In case HemoPill shows to be a reliable and effective tool, it can be safely introduced into clinical routine and unfold its then identified potential.

- Value of the information to be gained outweighs the risks involved

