### 6.1.11 Device Specific Considerations

#### Subject device

- Device size:
  - Length: 26.3 mm
  - Maximum diameter: 7 mm
  - Weight: 2 g
- Device model
  - HemoPill acute capsule: Software version 02.xx.yy
  - HemoPill Receiver: Software version 02.xx.yy
- Device settings and programming
  - HemoPill acute capsule: No settings or adjustments can be made during the trial. Software version 02.02.xx is implemented.
  - HemoPill Receiver: The HemoPill Receiver is used for activating a HemoPill acute capsule, for establishing a data connection between a HemoPill acute capsule and for displaying HemoPill acute measurements. Up to 50 data sets can be stored on the HemoPill Receiver. The HemoPill Receiver can be used to display, store, and delete data sets. The HemoPill Receiver cannot be used to alter or manipulate data sets.
- Frequency of exposure
  - HemoPill acute capsule: Once, duration of exposure from ingestion to excretion
  - HemoPill Receiver: Once, from establishing a data connection to a HemoPill acute capsule to conclusion of the measurement.

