## 8 Assessment of Safety

### 8.1 Specification of Safety Parameters

Safety parameters are identical to the safety endpoints defined in chapter 4.2.2:

Adverse events / complications associated with trial or control procedure, such as:

Trial procedure:

- Aspiration of the capsule on ingestion
- Delayed excretion, or failure to excrete the capsule (capsule retention)
- Obstruction of the digestive tract
- Injury to tissue structures during the passage of the HemoPill acute through the digestive tract.

Control procedure:

- Cardiopulmonary adverse events
- Infection
- Perforation
- Bleeding

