### 8.3 Time Period and Frequency for Event Assessment and Follow-Up

AEs and SAEs from trial procedure:

- Aspiration of the capsule on ingestion  
Immediate identification through extensive coughing. Localization and retrieval with bronchoscope.
- Delayed excretion, or failure to excrete the capsule (capsule retention)  
Identification
- Obstruction of the digestive tract
- Injury to tissue structures during the passage of the HemoPill acute through the digestive tract. In particular, this may involve:
  - Injury to the mucosa
  - Bleeding, e.g., variceal bleeding
  - Perforations

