## **8.5 Reporting Procedures – Notifying the Study Sponsor**

The study clinician will complete a SAE Form within the following timelines:

- All deaths and immediately life-threatening events, whether related or unrelated, will be recorded on the SAE Form and submitted to the IRB office and [name] within 24 hours of site awareness. See Section 1, Key Roles for contact information.
- Other SAEs regardless of relationship will be submitted to the [name] within 72 hours of site awareness.

All SAEs will be followed until satisfactory resolution or until the site investigator deems the event to be chronic or the adherence to be stable. Other supporting documentation of the event may be requested by the [name] and should be provided as soon as possible.

As a follow-up to the initial report, within the following 48 hours of awareness of the event, the investigator shall provide further information, as applicable, on the unanticipated event or the unanticipated problem in the form of a written narrative. This should include a copy of the completed Unanticipated Problem form, and any other diagnostic information that will assist the understanding of the event. Significant new information on ongoing unanticipated adverse effects shall be provided promptly to the study sponsor.

The study investigator shall complete an Unanticipated Adverse Device Effect Form and submit to the study sponsor and to the reviewing IRB as soon as possible, but in no event later than 10 working days after the investigator first learns of the effect. The study sponsor contact information is provided in Section 1, Key Roles.

As a follow-up to the initial report, within the following 48 hours of awareness of the event, the investigator shall provide further information, as applicable, on the unanticipated event or the unanticipated problem in the form of a written narrative. This should include a copy of the completed Unanticipated Problem form, and any other diagnostic information that will assist the understanding of the event. Significant new information on ongoing unanticipated adverse effects shall be provided promptly to the study sponsor.

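### Capsule retention, delayed excretion and later obstruction or distal injury are safety endpoints, but nothing after endoscopy is actively ascertained, so their prevalence over all participants is biased towards zero

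*Combined protocol and SAP*

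**What the plan says.** **Endpoints.** Section 4.2.2 lists "Delayed excretion, or failure to excrete the capsule (capsule retention)" among the trial-procedure safety endpoints, with obstruction and with tissue injury as the capsule passes through the digestive tract. Section 8.1 adds: "Safety parameters are identical to the safety endpoints defined in chapter 4.2.2". Section 2.4.1 places obstruction and retention under "Long-range risks".

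**Exposure.** Section 6.1.11 defines it as "HemoPill acute capsule: Once, duration of exposure from ingestion to excretion".

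**Observation.** The Protocol Summary gives participant duration as "Single visit, patient participation ends with conclusion of endoscopy", and receiver data collection stops at the same point. Section 5.5 states "No trial related follow-up is required".

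**Assessment period.** Section 8.3 is titled "Time Period and Frequency for Event Assessment and Follow-Up" but contains neither a period nor a frequency. Under retention it has one unexplained word (Identification). Under obstruction and injury it has no text on assessment. Section 8.7 repeats this list.

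**Analysis.** Sections 10.4.3 and 10.4.4 call for the prevalence of each safety endpoint relative to the total number of participants. Section 10.4.3 also allows a fraction of a subgroup, but no subgroup with known excretion status is defined.

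**The concern.** The plan reports a rate for outcomes that mostly cannot be known when observation stops. A participant whose excretion status was never checked enters the denominator and adds nothing to the numerator, so is treated as event-free. The error runs in one direction, towards zero.

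Section 2.1.1 says the study further investigates the device's safety and performance profile, and Section 2.4.1 names these as risks of the device. A line in the report saying that 0 of 50 capsules were retained could be read as evidence of no retention, when nobody looked.

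Aspiration, early obstruction and upper-tract injury visible at endoscopy are not affected. Neither are the primary accuracy endpoint or the sample size.

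**Working it through.** **1. The denominator.** Section 10.5 plans 43 evaluable participants and 14% dropout: 43 / (1 − 0.14) = 50. The planned total of 50 is reproduced, and it is the denominator for the safety prevalences.

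**2. The observation window.** Sections 4.1 and 6.1.5 set the latency from ingestion to endoscopy at 20 to 60 minutes. The documents give no endoscopy duration, so I assume 15 to 120 minutes.

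- Shortest window: 20 + 15 = 35 min
- Longest window: 60 + 120 = 180 min

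The interval of 1 hour to 3 days in Section 5.5 starts at screening, so it does not lengthen observation after ingestion.

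**3. Comparison with passage time.** Section 2.2.4.1 reports passage times from 8 tests in one volunteer: mean 79 h 01 min, range 51 h 25 min to 129 h 58 min.

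- Shortest passage: 51 × 60 + 25 = 3085 min
- 3085 / 180 = 17.1 and 3085 / 35 = 88.1
- Endoscopy length at which the window would reach the shortest passage, at 60 min latency: (3085 − 60) / 60 = 50.4 h

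The result does not depend on the assumed endoscopy time within any plausible range. As a separate comparison, the earlier clinical trial in Section 2.2.5 monitored excretion for up to 4 days (96 h), which is 96 / 3 = 32 times the longest window here.

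**4. What zero events in 50 would mean.** Let *p* be the true rate of a late event and *f* the fraction of such events that reach the site. The documents give neither, so both are assumptions. The expected observed prevalence is *p* × *f*, and the chance of seeing no event in 50 is (1 − *p f*)^50.

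| Assumed true rate | f = 1 | f = 0.5 | f = 0.25 | f = 0 |
|---|---|---|---|---|
| 2% | 36% | 61% | 78% | 100% |
| 5% | 8% | 28% | 53% | 100% |

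For 0 of 50, the exact two-sided 95% upper limit is 1 − 0.025^(1/50) = 7.1% with full ascertainment. This is a limit on *p f*, so the limit on *p* is 7.1% / *f*:

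- f = 0.5: about 14%
- f = 0.25: about 28%
- f = 0: no information, since 0 of 50 is then certain

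**The case against.** Safety is secondary here. It has no hypothesis and is only described, and the endpoint is worded as adverse events such as the listed items, so the list can be read as examples. No decision rests on a retention rate.

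Passive capture also exists:

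- Participants come from the investigators' own practices or inpatient care (5.4), and many will probably still be in hospital (7.2.2).
- Serious events and device-related adverse events are reported within 24 hours of the investigator's knowledge (8.4.1). Section 8.5 sends other serious events "within 72 hours of site awareness" and follows known ones to resolution.
- The safety review after each 10 patients names these very events (8.7).

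A symptomatic obstruction or perforation may well come to light this way. Finally, the passage times are from one volunteer, and the 17- to 88-fold ratio measures the gap in observation, not the bias.

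**What stands.** Capture is likely to be better for serious, symptomatic events than for silent retention, and the size of the bias is unknown. But every one of these routes needs someone to become aware of an event; none checks excretion status. An asymptomatic retained capsule would trigger nothing, and outpatients are eligible. A descriptive percentage is still misleading if its denominator consists of people whose status is unknown.

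Sections 2.2.1 and 2.1.3 say the capsule transmits for at least 21 days, in the latter so that excretion can be checked, yet no study section schedules or records that check. The instructions for use are a separate document and may describe one. Some pages, including the consent form, were not available for this review, but nothing in the available text points to a contact after endoscopy.

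**Conclusion.** The concern holds. The protocol defines late device events as endpoints, stops observing long before they can be determined, and still asks for their prevalence over everyone. The observation window is 35 to 180 minutes, against a shortest reported passage of 3085 minutes. Excretion status at the end of participation would be unknown for essentially every participant.

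This rests on an assumed endoscopy time of 15 to 120 minutes and on passage times from a single volunteer, which show direction and scale, not a population estimate. The direction of the bias is certain; its size cannot be computed from the documents. The point should be corrected before safety results are reported, but it does not threaten the primary analysis.

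**What to change.** Reconcile Sections 4.2.2, 5.5, 8.3, 10.4.3 and 10.4.4:

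- State that the trial-procedure safety endpoint covers events observed from ingestion to the end of endoscopy.
- State that excretion, retention and later obstruction or distal injury are not systematically assessed.
- List late events that reach the site as counts only, with no percentage over all participants.

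The Protocol Summary, Section 8.1 and Section 8.7 need matching edits, and the text on the 21-day transmission in Sections 2.2.1 and 2.1.3 should be squared with whatever is decided.

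This costs wording only. The price is a narrower safety statement: the study could not report a retention rate.

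If the sponsor chooses to record excretion status instead, it should fix the time point in advance and use only participants with known status as the denominator. That needs an amendment and a contact after endoscopy in what is now a single-visit design. A check with the receiver may need a return visit, because the device specification (Table 1) gives the radio link as short range.

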### ***5.6 Total Number of Participants and Sites***

Recruitment will end when approximately 50 participants are enrolled. It is expected that approximately 50 participants will be enrolled in order to produce 43 evaluable participants. Enrollment will take place solely at NYU Langone Health- Tisch Hospital.

### ***5.7 Participant Withdrawal or Termination***

#### ***5.7.1 Reasons for Withdrawal or Termination***

Participants are free to withdraw from participation in the study at any time upon request. An investigator may terminate participation in the study if:

- Any clinical adverse event (AE), laboratory abnormality, or other medical condition or situation occurs such that continued participation in the study would not be in the best interest of the participant
- The participant meets an exclusion criterion (either newly developed or not previously recognized) that precludes further study participation
- Decision for conducting endoscopy is reversed for any reason

### **5.7.2 Handling of Participant Withdrawals or Termination**

Participant withdrawal or termination does not affect subject safety. If a patient withdraws from participating in the clinical trial, scheduling of endoscopy is not affected. He or she will continue to be scheduled for endoscopy regardless of trial participation and therefore receive appropriate clinical care. Participation may be terminated by an investigator. As the trial procedure does not provide any immediate clinical benefits for a participant (see chapter 2.4.2), he or she is not negatively affected by termination. As the trial uses an intra-case relation of HemoPill measurement and endoscopy, any trial participant is evaluated on the basis of his or hers HemoPill measurement and endoscopic findings. Withdrawal or termination does therefore not require replacement of any individual participant for intra-individual comparison. The total number of participants is determined based on statistical considerations.

### **5.8 Premature Termination or Suspension of Study**

This study may be temporarily suspended or prematurely terminated if there is sufficient reasonable cause. Written notification, documenting the reason for study suspension or termination, will be provided by the suspending or terminating party to investigator, and regulatory authorities. If the study is prematurely terminated or suspended, the PI will promptly inform the IRB and will provide the reason(s) for the termination or suspension.

Circumstances that may warrant termination or suspension include, but are not limited to:

- Determination of unexpected, significant, or unacceptable risk to participants
- Demonstration of efficacy that would warrant stopping
- Insufficient compliance to protocol requirements
- Data that are not sufficiently complete and/or evaluable
- Determination of futility

Study may resume once concerns about safety, protocol compliance, data quality are addressed and satisfy the sponsor, IRB and/or FDA.

## **6 Study Agent (Study drug, device, biologic, vaccine etc.) and/or Procedural Intervention**

### **6.1.1 Acquisition**

#### Subject device

The HemoPill acute and HemoPill Receiver are Ovesco Endoscopy AG products, CE-labeled and marketed in the European Union. The HemoPill acute is provided sterile with a shelf life of 2 years. The HemoPill Receiver is provided non-sterile and is neither required nor intended to be sterilized. Packaging, sterilization and shipping of the HemoPill acute and HemoPill Receiver follow established and verified processes as required for medical devices in the EU. These processes are not altered for the devices provided for clinical trial purposes. The final, finished devices are supplied to NYU by Ovesco USA Inc.

